1 REVISION HISTORY

Revision	Date	Change
1	[REDACTED]	[REDACTED]
2	[REDACTED]	[REDACTED]
3	[REDACTED]	[REDACTED]
4	[REDACTED]	[REDACTED]
5	[REDACTED]	[REDACTED]
6	[REDACTED]	[REDACTED]
7	[REDACTED]	[REDACTED]
8	[REDACTED]	[REDACTED]
9	[REDACTED]	[REDACTED]
10	[REDACTED]	[REDACTED]
11	[REDACTED]	[REDACTED]
12	[REDACTED]	[REDACTED]
13	[REDACTED]	[REDACTED]
14	[REDACTED]	[REDACTED]
15	[REDACTED]	[REDACTED]
16	[REDACTED]	[REDACTED]
17	[REDACTED]	[REDACTED]
18	[REDACTED]	[REDACTED]
19	[REDACTED]	[REDACTED]
20	[REDACTED]	[REDACTED]
21	[REDACTED]	[REDACTED]
22	[REDACTED]	[REDACTED]
23	[REDACTED]	[REDACTED]
24	[REDACTED]	[REDACTED]
25	[REDACTED]	[REDACTED]
26	[REDACTED]	[REDACTED]
27	[REDACTED]	[REDACTED]
28	[REDACTED]	[REDACTED]
29	[REDACTED]	[REDACTED]
30	[REDACTED]	[REDACTED]
31	[REDACTED]	[REDACTED]
32	[REDACTED]	[REDACTED]
33	[REDACTED]	[REDACTED]
34	[REDACTED]	[REDACTED]
35	[REDACTED]	[REDACTED]
36	[REDACTED]	[REDACTED]
37	[REDACTED]	[REDACTED]
38	[REDACTED]	[REDACTED]
39	[REDACTED]	[REDACTED]
40	[REDACTED]	[REDACTED]
41	[REDACTED]	[REDACTED]
42	[REDACTED]	[REDACTED]
43	[REDACTED]	[REDACTED]
44	[REDACTED]	[REDACTED]
45	[REDACTED]	[REDACTED]
46	[REDACTED]	[REDACTED]
47	[REDACTED]	[REDACTED]
48	[REDACTED]	[REDACTED]
49	[REDACTED]	[REDACTED]
50	[REDACTED]	[REDACTED]
51	[REDACTED]	[REDACTED]
52	[REDACTED]	[REDACTED]
53	[REDACTED]	[REDACTED]
54	[REDACTED]	[REDACTED]
55	[REDACTED]	[REDACTED]
56	[REDACTED]	[REDACTED]
57	[REDACTED]	[REDACTED]
58	[REDACTED]	[REDACTED]
59	[REDACTED]	[REDACTED]
60	[REDACTED]	[REDACTED]
61	[REDACTED]	[REDACTED]
62	[REDACTED]	[REDACTED]
63	[REDACTED]	[REDACTED]
64	[REDACTED]	[REDACTED]
65	[REDACTED]	[REDACTED]
66	[REDACTED]	[REDACTED]
67	[REDACTED]	[REDACTED]
68	[REDACTED]	[REDACTED]
69	[REDACTED]	[REDACTED]
70	[REDACTED]	[REDACTED]
71	[REDACTED]	[REDACTED]
72	[REDACTED]	[REDACTED]
73	[REDACTED]	[REDACTED]
74	[REDACTED]	[REDACTED]
75	[REDACTED]	[REDACTED]
76	[REDACTED]	[REDACTED]
77	[REDACTED]	[REDACTED]
78	[REDACTED]	[REDACTED]
79	[REDACTED]	[REDACTED]
80	[REDACTED]	[REDACTED]
81	[REDACTED]	[REDACTED]
82	[REDACTED]	[REDACTED]
83	[REDACTED]	[REDACTED]
84	[REDACTED]	[REDACTED]
85	[REDACTED]	[REDACTED]
86	[REDACTED]	[REDACTED]
87	[REDACTED]	[REDACTED]
88	[REDACTED]	[REDACTED]
89	[REDACTED]	[REDACTED]
90	[REDACTED]	[REDACTED]
91	[REDACTED]	[REDACTED]
92	[REDACTED]	[REDACTED]
93	[REDACTED]	[REDACTED]
94	[REDACTED]	[REDACTED]
95	[REDACTED]	[REDACTED]
96	[REDACTED]	[REDACTED]
97	[REDACTED]	[REDACTED]
98	[REDACTED]	[REDACTED]
99	[REDACTED]	[REDACTED]
100	[REDACTED]	[REDACTED]

2 RELATED DOCUMENTS

Statistical Analysis Plan	CL 04502-004
Investigational Site Listing	CL 04502-003

Investigator Brochure:

Sonata Operators' Manual	LS 03818
Sonata Clinical Evaluation Summary	DMR 02768-001
Sonata System Summary of Product Safety Testing	LS 04566

3 ACRONYMS, INITIALS, and DEFINITIONS

ACOG	American College of Obstetricians and Gynecologists
AE	Adverse Event
ADE	Adverse Device Effect
AUB	Abnormal Uterine Bleeding
AUB-C	Abnormal Uterine Bleeding in the presence of Coagulopathy
AUB-L	Abnormal Uterine Bleeding in the presence of Leiomyomata
AUB-M	Abnormal Uterine Bleeding in the presence of Malignancy, Hyperplasia
CA	Competent Authority
CBC	Complete Blood Count
CRF	Case Report Form
Clinically Relevant Fibroids	Fibroids that are ≥ 1 cm and are classified as FIGO type 1 through type 4 fibroids as well as type 2-5 (transmural) fibroids
DVT	Deep Vein Thrombosis
EC	Ethics Committee
EDC	Electronic Data Capture
EQ-5D	Standardized instrument covering five quality of life dimensions for use as a health outcome measure
FIGO	International Federation of Gynecology and Obstetrics
FSH	Follicle-Stimulating Hormone
GCP	Good Clinical Practice
GnRH-a	Gonadotropin-Releasing Hormone Agonist
hCG	Human Chorionic Gonadotropin
HIPAA	Health Insurance Portability and Accountability Act
HMB	Heavy Menstrual Bleeding
HTN	Hypertension
HPV	Human Papillomavirus
HRQL	Health Related Quality of Life, a subscale of the UFS-QOL
IDE	Investigational Device Exemption
IFU	Instructions for Use
Intramural fibroid	A fibroid that is completely surrounded by myometrium
IRB	Investigation Review Board
IUD	Intrauterine Device
IUS	Intrauterine System
IUUS	Intrauterine Ultrasound
LCL	Lower Confidence Limit
LNG-IUS	Levonorgestrel Intrauterine System (Mirena®)
LOS	Length of Stay
MRgFUS	Magnetic Resonance-guided Focused Ultrasound
MRI	Magnetic Resonance Imaging
NRS	Numeric Rating Scale
NSF	Nephrogenic Systemic Fibrosis
OTE	Overall Treatment Effect
PBAC	Pictorial Blood Loss Assessment Chart

PE	Pulmonary Embolism
PT	Prothrombin Time
PTT	Partial Thromboplastin Time
PID	Pelvic Inflammatory Disease
RF	Radiofrequency
SADE	Serious Adverse Device Effect
SAE	Serious Adverse Event
SERM	Selective Estrogen Receptor Modulator
SIS	Saline-Infused Sonohysterography
SPRM	Selective Progesterone Receptor Modulator
SSS	Symptom Severity Score, a subscale of the UFS-QOL
Submucous fibroid	A fibroid that lies beneath and makes contact with the overlying endometrium to the extent that there is distortion of the endometrial cavity. These are subdivided into three categories: type 0, type 1, and type 2.
Subserous fibroid	A fibroid that makes contact with the uterine serosa (visceral peritoneum) to the extent that it distorts the external contour of the uterus. These are subdivided into three categories: type 5, type 6, and type 7.
Type 0 fibroid	An intracavitary pedunculated fibroid
Type 1 fibroid	A submucous fibroid that is < 50% intramural
Type 2 fibroid	A submucous fibroid that is ≥ 50% intramural
Type 3 fibroid	A fibroid that contacts the endometrium but is otherwise intramural
Type 4 fibroid	A fibroid that is entirely surrounded by myometrium
Type 5 fibroid	A subserous fibroid that is ≥ 50% intramural
Type 6 fibroid	A subserous fibroid that is < 50% intramural
Type 7 fibroid	A pedunculated subserous fibroid
Type 2-5 fibroid	A fibroid that is submucous and subserous, each with less than half their diameter in the endometrial and peritoneal cavities, respectively
TVUS	Transvaginal Ultrasound
UADE	Unanticipated Adverse Device Effect
UAE	Uterine Artery Embolization
UFS-QOL	Uterine Fibroid Symptom and Quality of Life Questionnaire
VAS	Visual Analog Scale
WPAI:SHP	Work Productivity and Activity Impairment Questionnaire: Specific Health Problem

4 **STUDY ABSTRACT**

A. STUDY TITLE

Evaluation of the Gynesonics System for Transcervical Treatment of Symptomatic Uterine Fibroids with Radiofrequency Ablation under Integrated Intrauterine Sonography Guidance

B. SHORT TITLE

Sonography-Guided Transcervical Ablation of Uterine Fibroids (SONATA)

C. PROTOCOL NUMBER

CL 04502

D. STUDY OBJECTIVE

To establish the safety and effectiveness of the Sonata System in the treatment of symptomatic uterine fibroids.

E. STUDY DESIGN

Prospective, longitudinal, multicenter, single-arm cohort study with the subject serving as her own control

F. STUDY DEVICE

Sonata® System

G. NUMBER OF SUBJECTS

147 treated subjects; at least 50% will be enrolled and treated within the United States

H. NUMBER OF SITES

Up to 27 investigational sites in the United States, Europe, and Mexico will participate in this study. At least half of the sites will be in the United States.

I. FOLLOW-UP

Subjects will be followed at 10 days, 30 days, 3 months, 6 months, 12 months, 24 months, and 36 months. The 24 and 36 month follow-up timepoints are included to gather longer-term data postmarket and will not be required to support a marketing application.

J. STUDY DURATION

Overall study duration (first subject enrolled through last subject exit) will be comprised of approximately 22 months of subject enrollment and 36 months of follow-up for a total duration of up to 58 months.

Study duration for an individual subject, once she provides her informed consent, will be up to 3 months for screening (including baseline measurements) and treatment, and 36 months for follow up for a total duration of approximately 38-39 months.

K. ENDPOINTS

Endpoints are reached at 12 months. Selected measurements will also be obtained at 10 days, 30 days, 3 months, 6 months, 24 months, and 36 months.

1) CO-PRIMARY ENDPOINTS

- (a) Reduction in menstrual blood loss (MBL) as assessed by pictorial blood loss assessment chart (PBAC)
- (b) Rate of surgical reintervention for heavy menstrual bleeding (HMB) due to treatment failure

2) SECONDARY ENDPOINTS

The following secondary endpoints will also be evaluated

- (a) Safety - adverse device effects
- (b) Reduction in total and perfused fibroid volume as measured by contrast-enhanced MRI
- (c) Change in the symptom severity score and health-related quality of life subscales of the Uterine Fibroid Symptom and Quality-of-Life (UFS-QOL) Questionnaire
- (d) Overall subject treatment outcome using the Overall Treatment Effect Scale (OTE)
- (e) Time to return to normal activity (days)
- (f) Subject Satisfaction
- (g) Change in general health outcome as measured with the EuroQOL EQ-5D questionnaire
- (h) Subject pain and tolerance of procedure
- (i) Mean institutional length of stay (LOS)
- (j) Occurrence of pregnancy and pregnancy outcome
- (k) Change in work productivity and activity impairment due to uterine fibroid symptoms as measured with the Work Productivity and Activity Impairment Questionnaire: Specific Health Problem (WPAI:SHP)

L. Selection Criteria

The criteria listed below shall be used to determine if a patient is eligible for entry into the study. A patient must meet ALL of the study inclusion criteria and NONE of the study exclusion criteria in order to be considered eligible for participation.

Inclusion Criteria

- 1) Are premenopausal
- 2) Are ≥ 25 and ≤ 50 years of age at time of enrollment
- 3) Have experienced heavy menstrual bleeding associated with fibroids (AUB-L) for at least the previous three months as reported by the subject
- 4) Have ≥ 1 and ≤ 10 fibroids of FIGO types 1, 2, 3, 4, and/or type 2-5, with diameter ≥ 1.0 cm and ≤ 5.0 cm as determined by credentialed transvaginal sonography or magnetic resonance imaging (MRI). Fibroids of type 5, 6, and 7 do not count toward the clinically relevant total, irrespective of size.
- 5) Have at least one type 1, type 2, type 3, or type 2-5 fibroid.
- 6) Pictorial blood loss assessment chart (PBAC) score ≥ 150 and ≤ 500 during a single baseline cycle
- 7) Consistent menstrual cycles of between 22 to 35 days in duration that meet the following requirements for at least 4 of the last 6 menstrual cycles prior to enrollment as reported by the subject:
 - (1) Variations in cycle length of no more than ± 4 days, and
 - (2) Bleeding duration of 3-10 days, in which the bleeding requires use of more than a pantiliner
- 8) Subject is not at material risk for pregnancy (not sexually active; has been sterilized; does not have a male partner or is in a monogamous relationship with a sterilized male partner; reliably uses barrier contraception, or oral or vaginal hormonal contraception. Subject is willing to maintain use or non-use of non-injectable hormonal contraception uniformly from 6 months pre-study through the 12-month follow-up period.¹ If a subject is on oral/vaginal hormonal contraception solely for bleeding control, or if a subject does not wish to commit to 12 months of consistent hormonal contraceptive use, subject must discontinue use as per the washout period specified in Appendix H.
- 9) Speaks and reads a language for which validated questionnaires are available
- 10) Willing and able to read, understand, and sign the informed consent form, to participate in the study and to adhere to all study follow-up requirements

¹ If changes in medical insurance would require a change in birth control preparation, then the study sponsor will provide the oral contraceptives taken at study enrollment free of charge until the one-year follow-up visit is completed.

Exclusion Criteria

- 1) Pregnancy, as determined by urine or serum hCG obtained within 24 hours prior to treatment with Sonata
- 2) Urgent need for surgery to treat fibroid symptoms
- 3) Desire for current or future childbearing
- 4) Presence of a tubal implant for sterilization
- 5) Postmenopausal by history
- 6) Presence of type 0 fibroids, unless < 1 cm in diameter and are unlikely to contribute to bleeding in the judgment of the investigator.
- 7) Presence of a single polyp ≥ 1.5 cm, or multiple polyps of any size, within the uterine cavity, or excision of polyps within three months of completing any screening procedures
- 8) Any fibroid of FIGO type 1, type 2, type 3, type 4, or type 2-5 with diameter > 5.0 cm as determined by transvaginal sonography or magnetic resonance imaging (MRI)
- 9) Bulk symptoms (pelvic pressure, frequent urination) that significantly interfere with normal daily activities in the presence of one or more fibroids of FIGO type 5, type 6, or type 7
- 10) Exclusive presence of fibroids that, despite meeting other eligibility criteria, are insufficient to explain the severity of symptoms in the judgment of the Investigator
- 11) Presence of clinically relevant fibroids that cannot be treated for technical reasons (e.g. cervical fibroid)
- 12) Presence of an extrauterine pelvic mass that has not been diagnosed as benign
- 13) IUD/IUS in situ within the washout period specified in Appendix H prior to undergoing any screening procedures
- 14) Not used
- 15) Previous procedure for fibroids or heavy menstrual bleeding other than myomectomy. Examples of excluded procedures: endometrial ablation,

- uterine artery/fibroid embolization, uterine artery occlusion, MR guided focused ultrasound, radiofrequency ablation.
- 16) Myomectomy by any route within 12 months prior to undergoing any screening procedures, or myomectomy > 12 months with less than 6 months of symptom relief
 - 17) Any abnormality of the endometrial cavity that, in the judgment of the Investigator, obstructs access of the Sonata Handpiece to the endometrial cavity or fibroids (e.g., significant intrauterine synechiae)
 - 18) Contraindication to MRI, including MR-incompatible implants, allergy to contrast media or claustrophobia, and weight that is above the limitation of the site-specific MRI scanner credentialed for the study
 - 19) Total uterine volume \geq 1000 cc as determined by transvaginal sonography
 - 20) Clinically significant adenomyosis based on sonography; presence confirmed by MRI (defined as more than 10% of the junctional zone measuring more than 10 mm in thickness as measured by MRI)
 - 21) Confirmed or suspected diagnosis of clinically relevant endometriosis
 - 22) One or more clinically relevant fibroids that are significantly calcified. If suspicion of calcification, refer to MRI. (Significant calcification is defined as

- being associated with a majority of the fibroid not showing enhancement on volume via contrast-enhanced MRI)
- 23) Previous pelvic irradiation
 - 24) Not used
 - 25) Renal insufficiency [serum creatinine \geq 1.5 mg/dL (132.6 μ mol/L)]
 - 26) Evidence of disorders of hemostasis (AUB-C) as assessed through structured interview and confirmed by hematologic evaluation consistent with a coagulopathy (see Appendix D)
 - 27) Abnormal cervical cytology that is unevaluated or untreated in adherence with national guidelines
 - 28) Endometrial hyperplasia (AUB-M), including simple hyperplasia without atypia, as determined by an endometrial biopsy within 12 months prior to enrollment
 - 29) Confirmed abdominal / pelvic malignancy within the previous five years
 - 30) Active pelvic infection (e.g., active salpingitis or other pelvic inflammatory disease) or current positive testing for pelvic gonorrhea or chlamydia; entry into the study would require a test of cure after treatment
 - 31) Use of a GnRH agonist, depomedroxyprogesterone acetate or other hormonally-relevant medication within the washout period as specified in Appendix H prior to undergoing any screening procedures
 - 32) Use of an antifibrinolytic agent while undergoing any screening procedures.
 - 33) Current use of anticoagulant therapy (warfarin derivatives or heparin)
 - 34) Chronic pelvic pain (disruptive for at least six months) or baseline pelvic or menstrual pain $>$ 6 as captured using the Numeric Rating Scale (NRS-11) as shown in Appendix J.2
 - 35) Chronic uncontrolled moderate and severe hypertension. (Chronic mild hypertension may be enrolled after obtaining medical clearance from a physician not participating in the study.)
 - 36) A hypoplastic or otherwise short uterus (distance from the top of the endometrial cavity to the external cervical os $<$ 4.5 cm, as determined by transvaginal sonography or prior uterine sounding)
 - 37) Major medical or psychiatric illness or other factors that, in the judgment of the Investigator may affect general health or subject's ability to adhere to the follow-up schedule or provide valid subject self-assessment data
 - 38) Any other reason for which, in the opinion of the Investigator, the individual study subject is not appropriate or suitable for participation in the clinical trial

5 INTRODUCTION

Uterine fibroids or myomata are the most common benign tumors in women. The prevalence of fibroids is approximately 20-25% in adult women, and the incidence increases with premenopausal age. The lifetime risk of developing fibroids is as high as 70% in white women and greater than 80% in women of African ancestry³. Most fibroids are asymptomatic. However, depending on the size and location of the tumors, fibroids can be symptomatic and may involve one or more of the following: heavy menstrual bleeding (HMB), dyspareunia, dysmenorrhea, anemia, pelvic/abdominal pressure, urinary retention, constipation, subfertility, pregnancy loss and preterm labor. Because they are prevalent and often symptomatic, fibroids impact the quality of life of millions of women and are associated with an increased utilization of health care resources involving treatments that are often invasive and expensive⁴.

Surgical options for treatment of myomata include hysterectomy and myomectomy, each of which can be performed via a number of approaches, such as laparotomy, laparoscopy, and hysteroscopy. Hysterectomy is the most common treatment for fibroids in the United States and, as with other surgical procedures, is associated with morbidity and mortality.

Pharmacotherapy with agents such as GnRH agonists is impractical as a long-term treatment due to their costs, side effects, and risks. Fibroids return to baseline size within weeks to months once such medications have been discontinued.⁵ However, GnRH agonists can be a useful adjunct to surgical procedures.

Uterine artery embolization (UAE) is an interventional radiology procedure that treats fibroids by blocking their blood supply. This involves catheterization of one or both femoral arteries and selective embolization of the uterine arteries. Despite its minimally invasive nature, UAE has been associated with post-procedure morbidity and complications, including post-embolization syndrome, rare uterine necrosis and, particularly in women 40 years of age and over, premature ovarian failure⁶.

6 STUDY DEVICE AND PROCEDURES

[figure not shown]
[figure not shown]
The Sonata™ System is intended for the transcervical treatment of symptomatic uterine fibroids, including those associated with heavy menstrual bleeding, under intrauterine ultrasound guidance.

[figure not shown]

6.1 Sonata System

The Sonata System consists of the following components:

6.2 Treatment Procedure

[Redacted text block containing multiple lines of blacked-out content under the heading '6.2 Treatment Procedure']

7 STUDY OBJECTIVE

The objective of this study is to establish the safety and effectiveness of the Sonata System in the treatment of symptomatic uterine fibroids.

8 STUDY DESIGN AND SAMPLE SIZE

The study is designed as a prospective, longitudinal, multicenter, single-arm cohort study with the subject serving as her own control. A baseline assessment of Menstrual Blood Loss (MBL), fibroid volume, fibroid-associated symptoms/quality-of-life (UFS-QOL), general quality of life (EQ-5D), and work productivity and activity impairment (WPAI:SHP) will be collected, which will allow a subject to serve as her own control.

The single-arm design is consistent with regulatory precedent for pivotal studies of devices intended for the treatment of uterine fibroids. Likewise, the co-primary endpoints of reduction in menstrual blood loss and reintervention are consistent with regulatory precedent for fibroid studies. Use of the pictorial blood loss assessment chart is consistent with regulatory precedent for other pivotal studies involving menstrual blood loss as a primary endpoint, such as studies of thermal endometrial ablation devices. The validity of the patient inclusion / exclusion criteria is supported by inclusion of patients with heavy menstrual bleeding (HMB) and fibroid types likely responsible for HMB, and exclusion of other causes such as adenomyosis or as indicated by presence of irregular bleeding.

The sample size for this study is at least 125 treated subjects to achieve 90% power with α level equal to 0.05 and an assumed success rate of 60%. To allow for 15% loss to follow-up, up to 147 women will be enrolled and treated. The statistical rationale for this sample size may be found in the Statistical Analysis Plan.

Overall study duration (first subject enrolled through last subject exit) will be comprised of approximately 22 months of subject enrollment and 36 months of follow-up post-treatment for a total study duration of up to 58 months.

Study duration for an individual subject, once she provides her informed consent, will be up to 3 months for screening (including baseline measurements) and treatment, and 36 months for follow-up for a total duration of approximately 38-39 months.

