19.1 Sample Size

A. Reduction in Menstrual Blood Loss (MBL) at 12 months

Ho: Population proportion of MBL success < 0.45

Ha: Population proportion of MBL success ≥ 0.45

In order to claim study success for MBL, the lower limit of the 95% confidence interval must be ≥ 0.45 .

Under the assumption that the MBL success rate is at least 0.60, a sample size of 125 subjects provides better than 90% power to demonstrate that the lower limit of the 95% confidence interval exceeds the pre-specified threshold.

B. Rate of surgical re-intervention for HMB

Ho: Population proportion of no surgical re-intervention success < 0.75

Ha: Population proportion of no surgical re-intervention success ≥ 0.75

In order to claim study success for surgical re-intervention, the lower limit of the 95% confidence interval must be ≥ 0.75 . Under the assumption that the no surgical re-intervention success rate is at least 0.9, a sample size of 75 provides better than 90% power to demonstrate that the lower limit of the 95% confidence interval exceeds the pre-specified threshold.

C. Allowance for expected dropout rate

To account for an assumed 15% subject dropout rate (subjects lost to follow-up at the 12-month visit), a sample size of 147 treated subjects will be enrolled and treated.

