5.6.7 Determination of Sample Size

SAS® PROC POWER was used to calculate the following sample sizes. The co-primary endpoint of Reduction in MBL at 12 months will be analyzed using 95% exact confidence intervals. In order to claim study success, the lower limit of the 95% confidence interval must exceed the pre-specified threshold (described in the table below).

Table 4: Determination of Sample Size

Co-Primary Endpoint	Lower Confidence Limit Success Criterion	Assumed Subject Success Rate	N to Achieve 90% Power
Reduction in MBL at 12 months	≥45%	60%	125
Rate of surgical reintervention for HMB due to treatment failure at 12 months	≥75%	90%	75

To account for an assumed 20% subject dropout rate (subjects lost to follow-up), a sample size of at least 125 and up to 150 treated subjects will be enrolled.

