5.6.8.2 Handling of Dropouts or Missing Data

Reduction in MBL at 12 Months

Missing 12-month menstrual blood loss data will be imputed using last observation carried forward (LOCF). Subjects which undergo surgical reintervention to manage fibroid symptoms prior to 12 months will be excluded from the Reduction in Menstrual Blood Loss analysis.

Surgical Reintervention for HMB due to Treatment Failure at 12 Months

Life-Table methods will be used to calculate the success rate and 95% confidence interval for the rate of surgical reintervention during 12 months. Therefore, subjects that are discontinued prior to 12 months for reasons other than surgical reintervention will be considered censored.

Sensitivity Analyses

Sensitivity analyses will also be conducted to examine the impact of missing data. A worst-case analysis (all missing data imputed as failures) and best-case analysis (all missing data imputed as successes) will be performed. In addition, a tipping point analysis will be performed.

Secondary Endpoint Analyses

No imputations will be made for missing secondary endpoint data.

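### The 90% power for the bleeding endpoint is stated for 125 women treated but holds for 125 women analysed, and the sample size makes no allowance for excluding reoperated women

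*Protocol*

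**What the plan says.** Protocol section 8 ties power to women treated: "The sample size for this study is at least 125 treated subjects to achieve 90% power". The calculation there takes 60% success and a 0.05 significance level. It then allows for 15% loss to follow-up, up to 147 women treated. Protocol 19.1 gives the same number without the word treated: "Under the assumption that the MBL success rate is at least 0.60, a sample size of 125 subjects provides better than 90% power". The success rule there is that "the lower limit of the 95% confidence interval must be ≥ 0.45", and SAP 5.6.7 fixes the method: "The co-primary endpoint of Reduction in MBL at 12 months will be analyzed using 95% exact confidence intervals".

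The only inflation in Protocol 19.1 is for dropout: "To account for an assumed 15% subject dropout rate (subjects lost to follow-up at the 12-month visit"). SAP 5.6.7 uses a different allowance, 20% dropout with 125 to 150 treated.

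SAP 5.6.8.2 sets two rules for the MBL analysis. Missing 12-month scores are filled by last observation carried forward (LOCF). Reoperated women are treated differently: "Subjects which undergo surgical reintervention to manage fibroid symptoms prior to 12 months will be excluded from the Reduction in Menstrual Blood Loss analysis". The planning value for the other co-primary endpoint, in Protocol 19.1, reads: "Under the assumption that the no surgical re-intervention success rate is at least 0.9".

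**The concern.** A woman who is reoperated before month 12 is treated but does not enter the MBL analysis. The plan expects up to 10% of such women and does not count them anywhere in the sample size. LOCF does not bring them back, because it applies to missing scores and these women are excluded by rule. So 125 treated cannot yield 125 analysed unless nobody is reoperated.

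MBL is the co-primary endpoint that drives the sample size (125, against 75 for reintervention). The power statement in Protocol section 8 sets a minimum number treated at which the trial may claim 90%, and that minimum does not support the claim on the plan's own planning value if 60% applies to the women analysed.

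**Working it through.** **Inputs.** Threshold 0.45 and assumed rate 0.60 (Protocol 19.1); exact 95% interval (SAP 5.6.7); reintervention at most 1 − 0.90 = 10% (Protocol 19.1); loss 15% and 147 treated (Protocol 8 and 19.1). Two-sidedness is inferred: it reproduces 125, whereas a one-sided 0.05 rule at 125 would give 0.958.

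**Formulas.** For n women analysed, r(n) is the smallest count x whose Clopper-Pearson lower limit, the 0.025 quantile of Beta(x, n − x + 1), is at least 0.45. Power(n) = P(X ≥ r(n)) with X ~ Binomial(n, 0.60). When women are removed at random, power is averaged over n ~ Binomial(N, k), with k = (1 − q)(1 − d(1 − f)). Here N is the number treated, q the share removed for reintervention, d the share lost, and f the share of lost women carried forward. Carried-forward women are given the same 60% success rate, which the documents do not state.

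**The plan's own figure.** n = 125: r = 68, power 0.914. n = 124: r = 68, power 0.897. From 125 upward, exact power stays at or above 0.90, so 125 reproduces as a number analysed and has no slack. The inflation also reproduces: 125 / 0.85 = 147.06.

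**With reoperated women removed.**

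| Treated | Removed q | Lost d | Lost carried forward f | Mean analysed | Power |
|---|---|---|---|---|---|
| 125 | 0 | 0 | – | 125 | 0.914 |
| 125 | 5% | 0 | – | 125 × 0.95 = 118.8 | 0.892 |
| 125 | 10% | 0 | – | 125 × 0.90 = 112.5 | 0.875 |
| 147 | 10% | 15% | none | 147 × 0.765 = 112.5 | 0.874 |
| 147 | 10% | 15% | half | 147 × 0.8325 = 122.4 | 0.900 |
| 147 | 10% | 15% | all | 147 × 0.90 = 132.3 | 0.920 |

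The third row is 0.8749 before rounding. At fixed sizes either side of its mean, n = 112 needs 62 successes (power 0.864) and n = 113 also needs 62 (power 0.886).

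**Sensitivity to what the 60% describes.**
- At 61% among those analysed, 125 treated with 10% removed gives 0.914.
- If 60% is the rate in all treated women with reoperated women as failures, the rate among the rest is 0.60 / 0.90 = 0.667, and power at n = 112 is 0.995.

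**A floor of 139 treated.** 125 / 0.90 = 138.9. With 10% removed, 139 treated gives 0.906 if every lost woman is carried forward, but 0.855 if 15% are lost and none is.

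**The case against.** A reader might infer that the planned trial itself, at 147 treated, has only 87% power. The documents do not support that. SAP 5.6.8.2 carries lost women forward, and Protocol Table 4 schedules PBAC diaries at 3 and 6 months that could be used. Carrying forward half of the lost women is enough to reach 0.90. The 0.87 case is still worth showing, because inflating 125 to 147 only makes sense if lost women are not analysed. The 0.92 case has its own weakness: SAP Table 2 has no PBAC before 6 months, and neither document says how a woman with no post-treatment score is handled.

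The second objection is stronger. The shortfall needs 60% to be the rate among women who were not reoperated, and the documents do not say so. Taking likely failures out of the denominator would tend to raise the rate in those left, and one percentage point closes the gap. This stands, and it is why the figures are conditional.

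Third, 10% is an upper value (success is at least 0.9). It concerns reintervention for heavy bleeding due to treatment failure, whereas the exclusion covers surgery to manage fibroid symptoms. The share removed could be lower or higher.

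Finally, 125 treated is not the planned enrolment. Protocol section 4 gives 147, and 19.1 uses 125 as the number before inflation, so section 8 may be loose wording. The gap is also small: exact power moves by about 2 points between n = 112 and n = 113. Both points limit the size of the problem. Neither makes the section 8 statement correct, and SAP 5.6.7 also gives 125 as the minimum number treated.

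**Conclusion.** The concern holds in a limited form. The sample size has no allowance for the SAP's exclusion of reoperated women, and 90% power belongs to 125 women analysed, not 125 treated. With 10% removed and 60% success among those left, 125 treated gives about 0.87 even with complete follow-up, roughly 3 points below the stated figure. With 5% removed it gives 0.89. At 147 treated the range is 0.87 to 0.92, depending on how many lost women are carried forward, so the documents do not show that the planned size is inadequate. All of this rests on the undefined population behind the 60%, on 10% as the share removed, and on carried-forward scores succeeding at the same rate. Under the other reading of the 60% there is no shortfall at all.

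**What to change.** In Protocol 8, Protocol 19.1 and SAP 5.6.7:

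- State that 125 is the number of women in the MBL analysis, and drop 125 treated as the basis for 90% power.
- State whether the 60% refers to all treated women or to those left after the reintervention exclusion.
- If it refers to those left, restate power at 147 treated as about 0.87 to 0.92 with 10% removed, depending on how many lost women are carried forward.
- Reconcile 15% and 147 (Protocol) with 20% and 150 (SAP). The SAP pair does not return 125: 150 × 0.80 = 120.

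Do not replace the floor with 139 treated, since that reaches 90% only under full carry-forward. The cost is wording in three places and a slightly less favourable stated power, with no extra patients.
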